##### ***Pregnancy Testing***

As mandated by the POMALYST REMS® program, all FCBPs must follow pregnancy testing requirements. In FCBP, pregnancy tests will be performed 10-14 days before, and within 24 hours of first study drug order. During the first treatment cycle, weekly pregnancy testing is mandated. Thereafter, pregnancy testing will be performed once every 4 weeks, during each cycle of treatment, preferably during the middle of the treatment cycle, or every 2 weeks for irregular menses.

##### ***Biorepository Samples***

Biorepository blood samples will be obtained at the following times: 1) screening visit, 2) randomization (baseline) visit, 3) at 12 and 24 week treatment period visits, 4) at the 4 week post-treatment (end of study) visit, and 5) early termination visit (if this occurs). These will be shipped to the lead PI's lab for storage. If a study visit is conducted remotely, sample collection for biorepository at that visit will be skipped.

---

#### **7.2.2 OTHER ASSAYS OR PROCEDURES**

---

##### **7.2.2.1 ASSESSMENT OF STUDY AGENT ADHERENCE**

Adherence to pomalidomide will be conducted by direct questioning and by pill counts at each study visit. Deviations from the prescribed dosage regimen should be recorded.

Patients who are significantly noncompliant may be discontinued from the study. A patient will be considered significantly noncompliant if he or she misses more than 5 consecutive days of study drug or more than 10 cumulative days of study drug during the study. Similarly, a patient will be considered significantly noncompliant if he or she is judged by the investigator to have intentionally or repeatedly taken more than the prescribed amount of study drug.

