#### 6.1.8.8 MUSCLE CRAMPING

In the case of muscle cramping, which may occur in some patients on higher doses of pomalidomide, treatment with over-the-counter quinine water as well as muscle relaxants such as cyclobenzaprine is allowed. If these do not diminish the intensity of symptoms to a tolerable level, the dose of pomalidomide may be reduced to 3 mg/day for two weeks, and the effect on cramping assessed. If this is unsuccessful in improving symptoms, the dose may be reduced to 2 mg/day. If symptoms remain intolerable, the patient will be removed from the study.

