#### 10.3 ANALYSIS DATASETS

**Modified Intention-to-Treat Analysis Dataset:** Randomized participants who took at least one dose of double-blind study medication and have at least one post-baseline efficacy measurement.

**Per-Protocol (PP) Analysis Dataset:** Randomized participants who complete the study with no major protocol violations and took at least 80% of the prescribed double-blind medication.

Patients who withdraw consent for further follow-up will be treated as lost to follow-up at the time that consent was withdrawn, and data will be used up to the time of study withdrawal.

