#### 10.4.5 ADHERENCE AND RETENTION ANALYSES

Missing data and missed visits will be monitored in real-time. In the event a scheduled visit is missed, site coordinators will contact the patient before the follow-up period closes to encourage them to at least obtain measurements relevant to the primary endpoint. For any missing data that do occur, we will record and describe the reasons the data are missing when reporting results.

In the event that one or more ESS or QOL score is missing during the treatment, or post-treatment periods, the MMRM analysis approach which assumes data are missing at random (MAR) will be used to compare treatments based on the available data and the correlation between observations with a person. To guard against bias if the MAR assumption is incorrect, sensitivity analyses will be explored, as specified above in section 10.4.2.

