**Analysis Method:** We conservatively conduct initial sample size calculations based on a T-test with equal variances (using the Power procedure within SAS). Since the primary analysis is an MMRM model with adjustment for baseline score, we next perform sensitivity power calculations which account for expected improvement in power based on the analysis plan. Data provided from the NOSE study indicated that the correlation between baseline and change from baseline at post-baseline visits is likely to be -0.4, and correlation between post-baseline visits is likely to be 0.5. Adjustment for baseline would reduce the standard deviation of the residual from 1.7 to 1.6. To evaluate power of the MMRM model in the face of increasing percent of missing data across study visits, we compute power using the formula by Lu, Luo, and Chen.

**Calculation and Sensitivity Analysis:** A total sample size of 159 patients (106 pomalidomide, 53 placebo) will provide 90% power to identify a treatment group difference in ESS change from baseline at 24 weeks of 1.0 with  $p<0.044$ , assuming a standard deviation of 1.7 and 10% early discontinuation rate. Power will remain above 80% if there is a substantially higher than expected study discontinuation rate of 30% (with 10% providing no post-baseline data): 81% based on a conservative

T-test, or 90% with the planned MMRM analysis. If the standard deviation is 1.8 instead of 1.7, the power for the planned MMRM analysis would be 91% with 10% discontinuation, and 87% with 30% discontinuation. Table 7 provides calculations for sample size selection, and Table 8 provides sensitivity of the power for the selected sample size.

Pomalidomide vs placebo Mean difference in ESS change from BL at W24	Std Dev of ESS change from BL at W24	Effect size = (mean difference) /SD	Power	Planned sample size with post-baseline data	Planned study early D/C rate	Total sample size.
-1.0	1.9	0.526	90%	180 (120:60)	10%	198 (132:66)
-1.0	1.8	0.556	90%	162 (108:54)	10%	178 (119:59)
-1.0	1.7	0.588	90%	144 (96:48)	10%	159 (106:53)
-1.0	1.6	0.625	90%	129 (86:43)	10%	141 (94:47)
-1.2	1.7	0.706	97%	144 (96:48)	10%	159 (106:53)
-0.7	1.7	0.412	62%	144 (96:48)	10%	159 (106:53)

Note: In each row, the bolded number was calculated. All other items in the row were fixed. Calculations based on a 2-sample T-test

**Table 7.** Sample size calculations for 2:1 randomization and Alpha = 0.044.

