5 ANALYSIS POPULATIONS

Randomization can occur either shortly before or at the baseline visit.

- If the screening visit was completed in-person, randomization can be completed before the baseline visit and study drug is ordered by the site from McKesson (manager of the study drug for Celgene and implementer of the Pomalidomide REMS system) to be shipped to the site so it is available at the site on the day of the baseline visit.
- If the screening visit was completed remotely, then eligibility is confirmed at the baseline visit and randomization occurs at baseline, and the drug is ordered to ship directly to the participant or to the site for dispensing to the participants within a few days of the baseline visit.

Under these scenarios, occasionally a randomized participant might withdraw consent before receiving the study medication from McKesson. Participants might also withdraw consent after receiving study medication but before the first follow-up visit and they may refuse to provide any follow-up assessments. Because these patients have no efficacy data to contribute to the analysis, they are excluded from the efficacy analysis populations, as follows:

Modified Intention-to-Treat Population (mITT)

The modified intention-to-treat population will comprise of all randomized participants who took at least one dose of the double-blind study medication AND have at least one post-baseline efficacy measurement.

Note that if a participant receives study drug sent by McKesson and does not return a full drug bottle to the site, it is assumed that they took at least some study drug.

Participants who receive study drug but do not complete the study will be used in all analyses for which data are available. Participants who withdraw consent for further follow-up will be treated as lost to follow-up at the time that consent was withdrawn, and data will be used up to the time of study withdrawal.

Per-Protocol Population (PP)

The per-protocol population will comprise of all randomized participants who complete the study with no major protocol violations and took at least 80% of the prescribed double-blind medication. Participants who were lost to-follow-up will be considered non-compliant for the purposes of the per-protocol population.

The blinded data review meeting identified the per-protocol exclusions as the following:

- Participants who did not take at least 34 pills of study drug (20%) for reasons other than AEs/side effects,

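### Protocol 7.2.2.1 lets sites end study participation, not only study drug, for modest nonadherence or for overuse, which can forfeit an otherwise obtainable week-24 ESS

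*Protocol*

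**What the plan says.** **The rule.** Protocol 7.2.2.1 (Assessment of Study Agent Adherence) states that "Patients who are significantly noncompliant may be discontinued from the study". It applies to a patient who "misses more than 5 consecutive days of study drug or more than 10 cumulative days of study drug during the study", or whom the investigator judges to have "intentionally or repeatedly taken more than the prescribed amount of study drug". The clause is permissive, and its object is the study, not the drug.

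**A parallel case.** Protocol 6.1.8.8 (Muscle Cramping) ends its dose-reduction steps with a mandatory version: "If symptoms remain intolerable, the patient will be removed from the study".

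**Other provisions on stopping drug.**
- 6.1.8.4: patients whose drug is held keep attending their regular visits.
- Tables 1B and 1D: the severe but non-fatal grades that end treatment take the patient off study drug permanently. Off study is entered only under Grade 5, which is death.
- 7.3.5 and Figure 3: after a permanent stop, the patient completes the current-cycle visit and an EOS visit 4 weeks later, and nothing more.
- 7.3.6 and Table 4: the early termination visit is for withdrawn consent only. No exit visit is named for a removal initiated by the site.

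**Analysis.** Protocol 10.4.2 fits an MMRM for change in ESS, assumes missing data are missing at random (MAR), and includes all data whatever treatment the patient took. The per-protocol set (10.3) requires study completion, no major violation, and that the patient "took at least 80% of the prescribed double-blind medication". SAP section 5 gives the blinded-review exclusion as "Participants who did not take at least 34 pills of study drug (20%) for reasons other than AEs/side effects".

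**The concern.** Under an intention-to-treat style analysis, imperfect adherence is part of what is being measured, so it should not be a reason to stop measuring. Section 7.2.2.1 allows a site to do that. A patient who misses capsules but is willing to attend can be taken out of the study, and every later ESS goes with them, including the primary value at week 24.

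Two things are at stake. First, data that section 10.4.2 would have used are never collected. Second, the loss depends on adherence. The MMRM conditions on treatment, site, baseline ESS and the ESS values already observed, but not on adherence. If adherence predicts later ESS beyond those variables, MAR fails for these patients. The model would then fill in their course from patients in the same arm who stayed, and who adhered better on average. The documents do not settle the direction of any bias: patients may miss doses because they feel no benefit, because of side effects, or because they feel well.

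**Working it through.** **1. The plan's own power figure.** Inputs from protocol 10.5 and Table 7: 106:53 randomised, 96:48 with data after 10% discontinuation, difference 1.0, SD 1.7, alpha 0.044, two-sided (10.4.1).
- Noncentrality = 1.0 / (1.7 × √(1/96 + 1/48)) = 3.33 on 142 df, giving power of 90.1%. The plan states 90%.
- At 30% discontinuation (74:37) the same formula gives 81.1%; the plan states 81%.
- At 20% (84:42) it gives 85.8%; the plan states 87%. The gap of about one point does not matter here.

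**2. How low the bar is.** Planned doses: 6 cycles × 28 = 168.

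| Criterion | Missed | Taken |
|---|---|---|
| 7.2.2.1, shortest single gap | 6 | 162/168 = 96.4% |
| 7.2.2.1, fewest scattered misses | 11 | 157/168 = 93.5% |
| Per-protocol, most misses allowed | 33 | 135/168 = 80.4% |

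The last row follows from 0.80 × 168 = 134.4, so at least 135 doses must be taken. The SAP's 34 pills is 34/168 = 20.2%, read here as pills not taken. The per-protocol limit is 33/6 = 5.5 times and 33/11 = 3.0 times the two triggers. A patient with 11 to 33 scattered misses meets the per-protocol dose criterion yet may be discontinued. Once discontinued, the patient has not completed the study and leaves the per-protocol set too.

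**3. Visits forfeited under 7.2.2.1.** There are 7 post-baseline ESS visits (C1 to C6 and EOS). The comparator is a patient who would have stayed on schedule. For discontinuation at visit Ck:

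| | C1 | C2 | C3 | C4 | C5 |
|---|---|---|---|---|---|
| Lost, no EOS visit (7 − k) | 6 | 5 | 4 | 3 | 2 |
| Lost, EOS done 4 weeks later (6 − k) | 5 | 4 | 3 | 2 | 1 |

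C6 (week 24) is lost in every column. These are upper bounds: they assume that the option is used and that every later visit would have been attended. Each lost week-24 value is 1/106 = 0.9% of the planned pomalidomide arm or 1/53 = 1.9% of the placebo arm.

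**4. If drug is stopped permanently.** The comparator is then 7.3.5, which keeps only the current-cycle and EOS visits. At most 2 visits are at stake, and week 24 is among them only for a stop in cycle 6. This covers the cramping rule in 6.1.8.8 and any overuser whose drug is stopped for safety.

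**5. Power.** The number lost is not in the documents, so the extra loss is an assumption. The retention column is a worst case in which that share of the active arm stays in and gains nothing (difference = 1 − f, 96:48).

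| Share f | f of the 144 lost | f of active arm kept, no benefit |
|---|---|---|
| 2% | 89.5% | 88.9% |
| 5% | 88.6% | 87.0% |
| 10% | 86.8% | 83.1% |

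Power moves little when patients are lost, and retention does not buy power. The argument for retention is that the estimate then describes the patients as randomised.

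**6. Directed holds.** Several holds that the protocol itself recommends or permits exceed 5 days: surgery (at least 7 days before and 14 to 21 after, 6.1.8.5), fatigue (1 to 2 weeks, 6.1.8.6) and neuropathy (up to 4 weeks, 6.1.8.12). A sensible reader would not count these as missed days, but 7.2.2.1 does not say so.

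**The case against.** The strongest reply is that the clause is discretionary and nothing shows that it was used. SAP section 5 names one discontinuation by investigator decision and one by joint decision, without reasons. If those were the only candidates, they would be 2 of 145 (SAP 7.6 site counts: 24 + 51 + 21 + 16 + 12 + 21), or 1.4%. The plan also allows for up to 30% discontinuation. SAP 9.3.1 adds a per-protocol analysis, plus control-based imputation and a tipping-point analysis. This limits the size and it stands. It does not make the rule harmless: the imputation analyses run only if the primary result is significant, and they address missing data after the fact.

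Some stronger readings are tempting, and the documents do not support them.
- *The protocol elsewhere only stops drug and keeps following patients.* Section 7.3.5 also ends follow-up after a permanent stop in cycles 1 to 5, with no week-24 visit. It is the wider source of week-24 loss.
- *Changing the study to study drug in 7.2.2.1 would recover week 24.* It does so only for patients kept on the visit schedule.
- *The gap between the 5- and 10-day triggers and 80% is an error.* One prompts action during conduct and the other defines a supportive analysis set. A conduct trigger may be stricter. The comparison shows only how little nonadherence is needed.
- *Section 10.4.5 is contradicted.* It asks sites, when a scheduled visit is missed, to contact patients and "encourage them to at least obtain measurements relevant to the primary endpoint". It does not govern discontinued patients. It shows the plan's intent, no more.
- *The cramping rule costs week-24 data in general.* Under 7.3.5 it does so only for a stop in cycle 6.

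**Conclusion.** The point holds for 7.2.2.1: as written, it permits an avoidable loss of the primary measurement for reasons linked to adherence, against the intention in 10.4.2. No other section corrects this. The loss of week 24 applies to patients who would otherwise have stayed on schedule and are discontinued at C1 to C5.

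The size is probably small. Power is hardly affected at the assumed losses of 2% to 10%, and how often the clause was used is unknown. The conclusion rests on two assumptions: that sites sometimes use the option, and that some of those patients would have attended C6. The cramping wording in 6.1.8.8 is a matter of consistency, with at most two visits at stake. Overall this is a cheap improvement, not a flaw that threatens the primary result.

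**What to change.** - **7.2.2.1:** state that noncompliance or overuse leads only to counselling or a study-drug decision (hold, reduce or stop), with visits and ESS continuing through C6 and EOS as 6.1.8.4 already provides for holds. Overuse can still lead to drug being stopped at once. State that protocol-directed holds are not missed days.
- **7.3.5:** if week 24 is also wanted after a permanent stop in cycles 1 to 5, this section must be changed to continue visits to C6. The 7.2.2.1 edit alone does not achieve that.
- **6.1.8.8:** replace removal from the study with permanent discontinuation of study drug followed by the 7.3.5 visits.
- **Reporting:** in the SAP 8.1 listing of withdrawal reasons, show separately any participant discontinued under 7.2.2.1 or 6.1.8.8. Rewording cannot recover visits already forgone, but the count would show whether the point mattered.

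The 7.2.2.1 and 6.1.8.8 edits cost a wording change, a few extra visits that are already on the schedule, and slightly more off-drug data in the mITT analysis. Off-drug follow-up is workable: SAP section 5 records two participants who stopped drug for adverse events and gave efficacy assessments for several months afterwards.

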#### 7.2.3 SPECIMEN PREPARATION, HANDLING, AND STORAGE

Biorepository samples will consist of one serum (SST) vacutainer tube, one citrate plasma tube and one EDTA plasma tube. At the randomization (baseline) visit, end of cycle 3 visit (week 12), end of cycle 6 visit (week 24) and early termination visit (if this occurs) we will also obtain one PAXgene blood RNA tube. When study visits involving biorepository sample collection are conducted remotely, sample collection will be skipped. Samples will be processed on site to isolate plasma and serum. PAXgene tubes do not require processing. Samples including the unprocessed PAXgene tube will be stored at -80° C and shipped to the PI's lab semi-annually. Samples to be shipped should include all samples collected from enrolled subjects up to the shipment date. Detailed instructions regarding processing, storing and shipping of biorepository and genetic testing samples will be described in the Manual of Procedures.

#### 7.2.4 SPECIMEN SHIPMENT

Shipping information, including shipping labels will be provided to each site. Samples for biorepository will be shipped overnight in dry ice and stored at -80°C upon receipt until the time of analysis.

### 7.3 STUDY SCHEDULE

#### 7.3.1 SCREENING

Each patient will require a screening visit to determine study eligibility. During the screening period the following information will be obtained.

- Informed consent of potential participant verified by signature on written informed consent
- Review enrollment criteria
- Review medical history
- Review of medication history
- Complete ESS with 3-month recall
- Documentation of packed red blood cell transfusions and/or iron infusions over the previous six months
- Performance of a detailed physical exam

- Collect blood for CBC, ferritin, iron and TIBC, renal and liver function, INR and aPTT (or PTT per local laboratory designation), and pregnancy testing for women of child bearing potential.
- Collect biorepository blood samples (if visit is in-person)
- Determine need for parenteral iron therapy based on results of iron studies.
- Provide participants with instructions for recording epistaxis duration between screening and enrollment/baseline visit.
- Schedule study visits for eligible patients.
- Provide participants with instructions for attending the baseline visit.

At the site PI's discretion, the screening visit may be conducted remotely. Obtaining signed informed consent prior to collecting any information for the study is mandatory for a remote screening visit as well. Physical examination may be limited to the extent possible at a remote visit; vital signs and biorepository sample collection will be skipped for remote screening visit. Screening laboratory studies may be obtained within 2 weeks before and after the screening visit.

Participants who do not initially meet eligibility criteria, but may meet criteria at a later time may be rescreened. Screening study procedures should be repeated per protocol and Manual of Procedures for rescreening. Baseline visit (if participant meets eligibility criteria) should be scheduled based on the rescreen date.

---

### 7.3.2 BASELINE/RANDOMIZATION

A period of at least 28 days after the screening visit will be required before the baseline/randomization visit, which must be conducted in-person. The baseline visit will be synonymous with the day of randomization and will include the following:

- Verification of inclusion/exclusion criteria
- Obtain ESS with 28-day recall
- Complete QOL instruments
- Perform pregnancy testing for women of child bearing potential
- Review of concomitant medications and adverse events
- Record vital signs, results of physical exam
- Collect laboratory samples for CBC, iron studies, and genetic testing
- Collect biorepository blood samples
- Collect epistaxis duration information
- Randomization and study drug order
- Study drug dispensation

Results from the laboratory assessments at baseline should not be used to re-establish eligibility criteria; study eligibility is determined by assessments completed at the screening visit.

If the screening visit was done in-person and study eligibility is confirmed, randomization and study drug order may be done 3-5 days before the baseline visit to ensure that study drug is available on site for dispensation on the day of visit. Patients may be instructed to initiate the drug the same day or the following day.

If the screening visit was done remotely, randomization and study drug order will be done at the baseline visit. A detailed physical examination will be performed at the baseline visit and biorepository sample collection tube will include PAXgene RNA tube in addition to the SST, sodium citrate and EDTA plasma tubes.

After randomization, study drug will be shipped overnight to the study site (or directly to the patient) from the experimental pharmacy. Patients will be instructed to initiate the drug upon receipt or the following day.

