#### 6.1.5 DOSING AND ADMINISTRATION

Females of child bearing potential must have two negative pregnancy tests to enter this trial, the first test being 10-14 days before and the second test within 24 hours prior to prescribing study drug. The dose of pomalidomide is 4 mg per day for days 1-28 of a 28 day cycle. For the purposes of this study, one cycle will be defined as 28 days. Subsequent cycles may begin within 5 days of completion of the

previous cycle, to allow time for patient assessment and provision of new drug to the study participant.

---

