 ESS will be a 3-month recall for these visits; for all other visits, it will be a 4-week recall.

-  Epistaxis Duration Diary will be collected at these visits and if applicable a new diary will be dispensed for the next set of epistaxis recording. For ET visit, diary will be collected if dispensed for the previous visit. See MOP for additional details.
-  Iron studies include ferritin levels, serum iron and total iron binding capacity.
-  One PAXgene RNA tube is included at these visits.
-  QOL questionnaires will include 3 NIH instruments (Neuro-QOL Satisfaction with Social Roles and Activities Short Form V1.1, PROMIS Emotional Distress - Depression Short Form V1.0 and PROMIS Fatigue Short Form V1.0) and a HHT specific questionnaire.
-  In FCBP, pregnancy tests will be performed 10-14 days before, and within 24 hours of first study drug order. During the first treatment cycle, weekly pregnancy testing is mandated. Thereafter, pregnancy testing will be performed once every 4 weeks, during each cycle of treatment, preferably during the middle of the treatment cycle, or every 2 weeks for irregular menses. For subjects completing an ET visit, pregnancy testing is only required if study medication was taken after the last pregnancy test.
-  Information on remaining drug and empty bottles will be collected over phone, email, or other means, if visit is remote.
-  Early Termination visits should be scheduled as soon as possible not to exceed 4 weeks post study drug discontinuation.
-  Strongly recommended that BL be scheduled 4 weeks after SC. Additional days up to 8 weeks to be used only for scheduling purposes.

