#### 8.4.5 REPORTING OF PREGNANCY

1. All FCBP are screened for pregnancy at the screening visit, and subsequently managed as mandated by the pomalidomide REMS. The REMS has the following requirements for pregnancy screening throughout the study.
2. Females taking Pomalidomide must avoid pregnancy during active treatment and for at least four weeks after taking pomalidomide.
3. Female patients of reproductive potential must either completely abstain from heterosexual sexual contact or must use two effective methods of contraception (at least one highly effective method and one effective method) at the same time (see Table 2 below).
4. The 2 effective contraceptive methods include using at the same time at least 1 highly effective method and at least 1 additional method of birth control every time they have sex with a male.

5. The 2 effective contraceptive methods must be started at least 4 weeks before POMALYST therapy, during therapy (including dose interruptions), and for at least 4 weeks following discontinuation of therapy.
6. The subject will undergo pregnancy testing twice prior to pomalidomide initiation. They must obtain a negative pregnancy test 10 to 14 days before first study drug order and again within 24 hours before study drug order even if continuous abstinence is the chosen method of birth control.
7. Pregnancy testing must occur weekly during the first four weeks of use.
8. During subsequent cycles, pregnancy testing must occur every 4 weeks if they have regular menses or every two weeks if menses are irregular.
9. The sensitivity of the pregnancy test should be at least 50mIU/ml.
10. Since oral estrogen may have a potential therapeutic effect in HHT, oral contraceptives are not considered an acceptable means of contraception during this study.

Table 2. REMS Program Contraceptive Methods		
Highly Effective Methods	Additional Effective Methods	Unacceptable Methods

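### The early drug-order option in Protocol 7.3.2 puts the baseline pregnancy test 3-5 days after the order, and no scheduled visit supplies the test required within 24 hours before it

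*Protocol*

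**What the plan says.** The rule for females of childbearing potential appears in four places, each tied to the prescription or order and not to a visit.

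- Protocol 8.4.5, item 6: "They must obtain a negative pregnancy test 10 to 14 days before first study drug order and again within 24 hours before study drug order".
- Protocol 6.1.5, as a condition of entry: "the first test being 10-14 days before and the second test within 24 hours prior to prescribing study drug".
- Protocol 7.2.1.2: "pregnancy tests will be performed 10-14 days before, and within 24 hours of first study drug order".
- Protocol Table 4, footnote 10, repeats the 7.2.1.2 wording.

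Inclusion criterion 9 also binds these patients to the REMS testing schedule and points to 8.4.5.

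The visit schedule is laid out differently. Protocol 7.3.1 lists a pregnancy test among the screening blood tests. Protocol 7.3.2 lists among the baseline procedures: "Perform pregnancy testing for women of child bearing potential". The Table 4 pregnancy-test row marks screening and baseline as the only visits before treatment. On spacing, 7.3.2 says: "A period of at least 28 days after the screening visit will be required before the baseline/randomization visit"; Protocol 4.1 sets the upper limit at 56 days.

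For patients screened in person with eligibility confirmed, 7.3.2 then adds that "randomization and study drug order may be done 3-5 days before the baseline visit", so that drug is on site for the visit. SAP section 5 describes the same route.

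**The concern.** The early-order sentence moves the order but leaves the pregnancy test where it was. Someone working from the 7.3.2 list and the Table 4 columns would find a test at screening and one at baseline. On the early route the second of these comes after the order it should precede. Nothing in 7.3.2 says that the option works differently for females of childbearing potential, and it does not refer to 8.4.5.

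Teratogenicity is the first risk listed in Protocol 2.3.1, and that section says that precautions are built into the protocol. The schedule should therefore show where the required tests fall.

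There is also a smaller consequence for the analysis. If a baseline test is positive after an early order, the patient is already randomised. If she then takes no drug, she is outside the modified intention-to-treat population (Protocol 10.3, SAP section 5). Section 7.3.2 says that baseline laboratory results are not to be used to reopen eligibility, and it does not say how a positive pregnancy test is handled.

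**Working it through.** The plan gives no figure to reproduce, so the check is a day count.

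**Inputs**
- Screening visit = day 0.
- Baseline visit B = day 28 to 56 (Protocol 4.1, 7.3.2), which is 56 − 28 + 1 = 29 possible days.
- Lead L = days from order to baseline: 0 for an order at baseline; 3, 4 or 5 for an early order (7.3.2).
- Order day O = B − L.
- Required tests: 10-14 days before O, and no more than 24 hours before O (8.4.5; 6.1.5 ties the same windows to prescribing).
- Screening laboratory tests may be drawn up to two weeks either side of the screening visit (7.3.1).

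**Step 1: the 24-hour test.** The baseline test falls B − O = L days after the order. For L = 3 to 5 that is 3 × 24 = 72 to 5 × 24 = 120 hours after. It fails the before-order wording of 6.1.5 and 8.4.5. It also fails the looser wording of 7.2.1.2 and footnote 10, which does not state a direction. Section 7.3.2 gives no laboratory window that would move the baseline test; the one-week window in 7.3.3 is written for treatment follow-up visits. For L = 0 the baseline test can meet the rule.

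**Step 2: the 10-14 day test, drawn on the screening day.** The gap to the order is O − 0 = B − L.

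**Step 3: the same test, drawn as late as 7.3.1 allows (day +14).** The gap is B − L − 14. It must not exceed 14, so B ≤ 28 + L.

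| Lead L | Screening-day test to order (days) | In 10-14 window? | Baseline days at which a test by day +14 can meet the window |
|---|---|---|---|
| 0 | 28-56 | No | 28 only (1 of 29) |
| 3 | 25-53 | No | 28-31 (4 of 29) |
| 4 | 24-52 | No | 28-32 (5 of 29) |
| 5 | 23-51 | No | 28-33 (6 of 29) |

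The lower limit of 10 days does not bind. In the tightest case (B = 28, L = 5, order on day 23), a test on days 9-13 is 10-14 days before the order.

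**Reading the two results together.** The 24-hour mismatch is caused by the early order and affects every early order. The 10-14 day mismatch comes from the 28-56 day spacing of screening and baseline and is there without an early order. An early order makes that window slightly easier to reach.

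**The case against.** The strongest reply is that the mandatory rule governs. The early order is permissive and is conditional on confirmed eligibility. Eligibility includes criterion 9, and 6.1.5 makes two negative tests a condition of entry. Because 7.2.1.2, 8.4.5 and footnote 10 tie the tests to the order date, the windows move with an early order. A site can satisfy every section by testing between visits, as it must in any case for the weekly tests in cycle 1. This stands. It means that the required testing is in the protocol and that the defect is one of scheduling and cross-reference.

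A reader might infer that a site using the early route would order drug with neither test done. The documents do not support that: nothing in 7.3.2 removes the rule. The Manual of Procedures and the REMS text are not available here, so site practice cannot be judged.

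A reader might also infer that the screening test can never fall in the 10-14 day window. That is wrong too. The 7.3.1 laboratory window allows it at the short end of the interval, and Table 4 footnote 13 strongly recommends scheduling baseline four weeks after screening, which is that end.

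Finally, on the early route the drug is shipped for dispensing at the baseline visit, where a pregnancy test is also listed. That bears on exposure, but not on the requirement, which is set by the order or prescription. Nor does 7.3.2 say that dispensing waits for the result.

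None of these points supplies a visit for the 24-hour test when the order is placed early.

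**Conclusion.** The inconsistency is real, and it is narrower than a gap in testing. With an early order, the baseline test is 3-5 days too late to be the second pre-order test, and Table 4 has no visit column that provides one. Independently, a screening-day test misses the 10-14 day window in every case. The laboratory allowance brings it within reach only for baseline on about days 28-33 (early order) or on day 28 (order at baseline), out of a permitted 28-56.

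This rests on three assumptions: the 3-5 days are calendar days, the baseline test is done on the day of the visit, and the 7.3.1 laboratory window covers the screening pregnancy test listed there. The patients concerned with the 24-hour point are females of childbearing potential screened in person whose order is placed early; the documents do not give their number. The matter should be corrected because the drug is teratogenic and the correction is simple. It does not show that any patient went untested.

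**What to change.** Reconcile Protocol 7.3.2 and the Table 4 pregnancy-test row with 6.1.5, 7.2.1.2 and 8.4.5. The revised text should:

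- state how the early-order option applies to females of childbearing potential;
- show where both pre-order tests fall relative to the screening and baseline visits;
- use one wording for the 24-hour window, including its direction and whether it runs from prescribing or from ordering;
- say how a positive baseline test is recorded when the patient has already been randomised;
- settle, in the same edit, the statement in 7.3.2 that baseline is the day of randomisation, which the early option contradicts.

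The clinical team and the REMS requirements decide which timing applies; this review takes no view on it. The cost is a protocol clarification and a memo to sites. It adds no test beyond those already required and does not alter the sample size or the analysis.
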